5.2 Discontinuation of Study Intervention

The study involves one-time administration of ABO matched COVID-19 convalescent plasma.

5.3 Participant Discontinuation/Withdrawal from the Study

Study participant is free to withdraw consent from participation in further data collection at any time during the study. If a patient withdraws consent, survival data will still be collected. No additional data will be collected.

5.4 Lost to Follow-Up

The protocol follows the subjects only for a limited interval. It is not anticipated that study participants will be lost to follow-up.

6.0 Statistical and Quantitative Analysis

6.1 Determination of Sample Size and Statistical Analysis

Group sequential design is employed for each hypothesis that analysis will be performed after enrolling and observing outcomes of one-third of maximum sample size. Our design includes two interim analyses and a final analysis for each hypothesis. The Pocock method is used to determine sample size and each study is sized to maintain the power of 80% and overall type I error 5%. To calculate the sample size, the large-sample Z test for a proportion is utilized for each analysis.

	Enrollment at stage 1	Enrollment at stage 2	Enrollment at stage 3	Maximum enrollment	Expected enrollment for projected proportion
Study group 3	76	76	76	228	159
Study group 4	73	73	73	219	152

Group 3

For high-risk COVID-19 infected patients that present with early mild or non-severe disease the estimated percent who will develop severe disease is 27% for those over age 65. There is insufficient data on patients who have coexisting severe immune compromised status; however, for patients that presented with diabetes or heart disease/hypertension risk was 16% - 30%, respectively. Assuming a reported risk of progression of 25%, it is postulated that the infusion of convalescent plasma will reduce the probability for progression to severe disease by a factor of 0.35 to 16.3% or lower. We will carry out 3-stage of enrollment and 76 patients are enrolled in each stage. The interim analysis will be performed after enrolling and observing outcomes of 76 patients. Our design leads to the maximum size of 219 patients after completing 3-stage of enrollment and the expected size is 159 patients.

Group 4

Among healthcare workers 14.8% of cases were classified as evolving to severe or critical per the Chinese epidemiological review. ^{24,25} It is postulated that the infusion of convalescent plasma will reduce the probability for progression from asymptomatic, mild or nonsevere disease to that of severe disease will be reduced by a factor of .5 to 7.5% or lower. We will carry out 3-stage of enrollment and 73 patients are enrolled in each stage. The interim analysis will be performed after enrolling and observing outcomes of 73 patients. Our design leads to the maximum size of 219 patients after completing 3-stage of enrollment and the expected size is 152 patients.

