4.1.1 Group 3: High Risk Patients with Mild or Non-severe Disease

- 1. Mild Disease: upper respiratory symptoms, cough, gastrointestinal symptoms (emesis, diarrhea, abdominal pain) or fever; but no radiograph evidence for viral pneumonitis.
- 2. Non-severe Disease: Chest radiographic changes compatible with COVID-19 disease, but no signs of respiratory compromise or hypoxemia.
- 3. High Risk condition must include one of the following: Immunocompromised (e.g. neutropenia, active chemotherapy for cancer or hematological malignancy, less than 12 months after undergoing allogeneic hematopoietic stem cell transplant or 100 days from autologous hematopoietic stem cell transplant, on systemic immunosuppressive therapy, history of solid organ transplant and poorly controlled HIV disease (e.g. CD4, 250/uL, recurrent opportunistic infections), insulin dependent diabetes mellitus, moderate to severe asthma history, severe COPD (DLCO < 60), morbid obesity (BMI ≥ 40),age ≥ 65 years, hypertension, moderate or severe cardiac disease (eg. Cardiomyopathy, CHF, moderate or

- severe valvular stenosis, ischemic heart disease), patients with severe renal disease (e.g. on dialysis), or liver disease
- 4. Informed consent signed within 14 days of symptoms developing for mild disease. For patients in the non-severe cohort, the time to consent must be within 14 days of positive chest x-ray or 14 days of first symptom whichever is longer (maximum 14 days to enrollment).

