6.3 Statistical Analysis

We will perform intention-to-treat analysis to analyze outcomes of all enrolled patients. The primary analysis is to evaluate the CRF or disease progression rate against the null proportion. We plan to perform two interim analyses and one final analysis. The first interim analysis will be performed after enrolling and observing outcomes of one-third of maximum sample size. At an interim analysis, CRF or disease progression rate will be reported, together with a score confidence interval for the rate. The critical value used to evaluate the confidence interval is 2.289 based on the Pocock method. We will compare the upper limit of the confidence interval with the assumed null proportion. We will conclude efficacy of the treatment if the upper limit is less than the null proportion and terminate enrollment for the relevant study group. If the upper limit is greater than the null proportion, we will proceed to the second stage of enrollment and then perform the second interim analysis on the cumulative data. The same evaluation will be replicated in the second interim analysis, as well as in the final analysis should we proceed to this step.

After completing the trial, we will conduct secondary analysis to compare outcomes of this trial with published historical experience. We will use the score test for comparing two proportions in each evaluation. We will report both p value and 95% score confidence interval for difference between two proportions.

It is acknowledged that COVID-19 viral pandemic outbreak remains dynamic. Epidemiological update reports from the CDC may result in reassessment for case fatality rates as well as case rates for disease progression used in our study design that may require adjustments in sample size determinations at the interim analysis as independently allowed by the biostatistician.

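### Group 3 efficacy is judged against one assumed 25% rate, and no planned primary-endpoint analysis relates that rate to the high-risk mix enrolled; the text maximum of 219 should also read 228

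*Combined protocol and SAP*

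**What the plan says.** Section 6.1 (Group 3) cites an untreated risk of severe disease of 27% for patients over 65. It adds that "for patients that presented with diabetes or heart disease/hypertension risk was 16% - 30%, respectively", read here as 16% for diabetes and 30% for heart disease or hypertension. On immune compromise it says: "There is insufficient data on patients who have coexisting severe immune compromised status". It then moves to "Assuming a reported risk of progression of 25%, it is postulated that the infusion of convalescent plasma will reduce the probability for progression", with a target of 16.3%.

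Section 4.1.1 opens its list with "High Risk condition must include one of the following: Immunocompromised" and goes on to insulin-dependent diabetes, asthma, COPD, morbid obesity, age 65 or over, hypertension, and cardiac, renal and liver disease. Any one qualifies, and there are no quotas.

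Section 6.3 gives the decision rule, applied at up to three looks with critical value 2.289: "We will conclude efficacy of the treatment if the upper limit is less than the null proportion". It also foresees, from CDC reports, a "reassessment for case fatality rates as well as case rates for disease progression used in our study design", and after the trial "we will conduct secondary analysis to compare outcomes of this trial with published historical experience".

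On size, the Group 3 text of 6.1 states: "Our design leads to the maximum size of 219 patients after completing 3-stage of enrollment and the expected size is 159 patients". The table above it and the Overview of Study Design both give a maximum of 228.

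**The concern.** There is no concurrent control, so the 25% carries the whole primary comparison. It is a fixed number, while the untreated risk of the patients enrolled depends on which conditions they bring. If their average untreated risk is below 25%, inert plasma will pass more often than at 25%. If it is above 25%, for instance because most patients are over 65 or hypertensive, the rule is conservative and a real relative reduction is missed more often. A reader of either result would want to know which way the enrolled group leaned, and the plan does not provide for showing this.

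**Working it through.** **1. The plan's own size.** Inputs from 6.1 and 6.3: null 0.25, target 0.163, power 80%, overall error 5% (two-sided), Pocock with three looks and c = 2.289.

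Fixed-sample size with null variance: (1.960 + 0.842)² × 0.25 × 0.75 / (0.25 − 0.163)² = 194.4. Multiplying by the three-look Pocock inflation of about 1.166 gives 226.7, so 76 per stage and 3 × 76 = 228. Multivariate-normal integration gives power 0.802 and expected size 159.7. The planned 228 and 159 therefore reproduce. The 219 in the Group 3 text does not: 219 = 3 × 73, which is Group 4's figure.

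**2. Stopping bounds.** The upper score limit is

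U = [p̂ + c²/2n + c√(p̂(1 − p̂)/n + c²/4n²)] / (1 + c²/n).

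For 10/76: (0.1316 + 0.0345 + 0.0952) / 1.0689 = 24.44%, below 25%. In the same way 25/152 gives 24.42% and 42/228 gives 24.98%. Efficacy is declared at no more than 10/76, 25/152 or 42/228 events.

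**3. Probability of declaring efficacy.** With Xₖ the cumulative events at look k and p the true rate on treatment,

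P = P(X₁ ≤ 10) + P(X₁ > 10, X₂ ≤ 25) + P(X₁ > 10, X₂ > 25, X₃ ≤ 42),

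computed by exact binomial recursion. For inert plasma p is the untreated rate; for a 35% relative reduction it is 0.65 times that rate.

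| True untreated rate | Assumed mix giving it | Inert plasma declared effective | Power, 35% reduction |
|---|---|---|---|
| 23% | (16 + 30)/2 | 7.9% | 94% |
| 24.3% | (27 + 16 + 30)/3 | 3.4% | 89% |
| 25% | the null | 2.2% | 85% |
| 27% | all over 65 | 0.5% | 70% |
| 30% | all heart disease/hypertension | 0.06% | 42% |

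The inert-plasma figure passes 5% only when the true untreated rate is below about 23.7%. If the treated rate is held at 16.3% instead of 35% below the untreated rate, power is 85% whatever the untreated rate. Using 73 per stage, as the 219 would imply, changes little: 2.0% at 25% and 7.4% at 23% for inert plasma, and power of 68% at 27%.

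**4. Does anything planned relate 25% to the mix?**
- The historical or matched comparison in 6.2.1 is for secondary endpoints; progression is the primary endpoint (3.1.1).
- The post-trial comparison in 6.3 is a two-proportion score test with no case-mix adjustment stated.
- The reassessment in 6.3 is triggered by external CDC reports. Its stated consequence is a sample-size adjustment, not a rule for the null or for the enrolled mix.
- Charlson index, performance score and immunosuppression are collected (3.1.3.5, 5.1.1) but not linked to the 25%.

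**The case against.** The case for leaving the plan alone is strong. Every single-arm trial depends on its null, and this one says so: the comparison is with historical experience, and the rate is openly called assumed. The value is reasonable. It lies inside the cited range, the unweighted mean is 24.3%, and weights of 50/25/25 on 27%, 16% and 30% give 13.5 + 4 + 7.5 = 25% exactly. It is also described as a reported risk, so it may come from a source not named there; the missing derivation is absent detail, not an error. All of this stands.

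A reader might infer that the 25% is set too high and the error rate is inflated. The documents do not support that. Inert claims exceed 5% only below about 23.7%, which needs a group heavy in the 16% rate. Section 4.1.1 admits only insulin-dependent diabetes, for which no separate rate is cited, and it also admits older, hypertensive and cardiac patients, who would pull the average up. Reading 16% and 30% as two condition-specific rates is itself an interpretation.

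A reader might also infer that patients with no cited rate can be bounded by 16% and 30%. Nothing in the documents makes those values limits for, say, immunocompromised patients.

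Finally, 6.3 already reports the progression rate with a score interval, which a reader can set beside any cited rate. What that does not show is who was enrolled. The baseline worksheet named in 5.1.1 is not in the documents, so the qualifying conditions may already be recorded; no planned analysis uses them for this purpose.

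**Conclusion.** The point holds as a limited one, worth considering: for the primary endpoint, no planned analysis relates the assumed 25% to the high-risk mix enrolled in Group 3. A two-point shift inside the cited range moves the chance of declaring inert plasma effective from 2.2% to 7.9% (at 23%) or 0.5% (at 27%). Power for a 35% relative reduction falls from 85% to 70% at 27%, and to 42% at 30%. These figures rest on assumed mixes, on the reading of the 16% and 30%, and, for the power loss, on a constant relative effect. They show sensitivity in both directions; they do not show that 25% is wrong or that the error rate will exceed the plan's level.

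The Group 3 maximum is a plain inconsistency. The table, the overview and 3 × 76 all give 228, against 219 in the text.

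**What to change.** 1. In 6.1, change the Group 3 maximum in the text from 219 to 228.

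2. Keep the 25% null and the stopping rule. In 6.3, pre-specify a sensitivity report for the look at which Group 3 ends:
   - the enrolled mix by 4.1.1 condition, with all qualifying conditions recorded at baseline;
   - for patients with each condition that has a cited rate, the progression rate with its score interval, beside that cited rate;
   - the overall upper limit beside the case-mix-weighted cited rate for the rated patients, with a rule stated in advance for patients who have several rated conditions;
   - the share of patients with no cited rate, with no rate imputed to them.

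The report qualifies the primary conclusion, positive or negative. It carries no pass/fail label and does not affect stopping.

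The cost is a few sentences, complete baseline recording of qualifying conditions and a weighted average, with no new visits. There are downsides. Subgroups will be small: if Group 3 stops at 76, three equal groups hold about 25 patients each. The cited rates are uncertain, and the overall limit and the weighted rate cover different patients when the unrated share is large, so the comparison may be inconclusive. Some true efficacy claims will carry a caveat. If every patient were rated and a weighted rate of 24.3% were exactly right, the upper limit would not fall below it in 1 − 0.6505/0.8903 = 27% of efficacy claims made under a true 35% reduction. Many of these would be near-misses, such as 24.44% against 24.33%, which is why the figures should be shown without a label. Power lost when the true untreated rate is above 25% is not recovered.

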Use of Convalescent Plasma Collected From Donors Recovered From COVID-19 Virus
Disease for Transfusion, as an Empirical and Preemptive Treatment during Viral
Pandemic Outbreak

Principal Investigator: [name]

Protocol version: 12/7/2020

Protocol Summary

Study Title: Use of Convalescent Plasma Transfusion, Collected From Donors Recovered From COVID-19 Virus Disease, as an Empirical and Preemptive Treatment during Pandemic Outbreak

Phase II

Expected Numbers of Patients:

Group 3: High risk patients n=159
Group 4: Health Care Providers n=152

Study Objectives:

- 1. To transfuse COVID-19 infected patients with convalescent plasma and to observe whether this will result in a significant improvement in clinical outcome in comparison to historical experience. Patients eligible include the following study groups:
- **Group 3:** As preemptive therapy for High Risk Patients who present with mild or non-severe COVID-19 infection.
- **Group 4:** As preemptive therapy for health care providers who have developed asymptomatic, mild or non-severe COVID-19 infection.
- **a. Primary objective** is whether infusion of convalescent plasma will reduce the probability of progressing to severe or critical disease significantly lower than the reported case rate (for Group 3 and 4, respectively).
- **b. Secondary objectives** are to determine if infusion of convalescent plasma will impact the patient's clinical course including days in hospital, days requiring ICU care, days on mechanical respirator/BIPAP, days on non-mechanical oxygen support, days with pneumonia, fever, and viral clearance.

Overview of Study Design

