Group sequential design is employed for each hypothesis that analysis will be performed after enrolling and observing outcomes of one-third of maximum sample size. Our design includes two interim analyses and a final analysis for each hypothesis. The Pocock method is used to determine sample size and each study is sized to maintain the power of 80% and overall type I error 5%. To calculate the sample size, the large-sample Z test for a proportion is utilized for each analysis. The maximum number of enrollment for the four groups are: Group 1: 81, Group 2: 423, Group 3: 228 and Group 4: 219. Due to the likelihood that we may terminate a study for efficacy after an interim analysis, the expected numbers of enrollment for the four groups are 56, 296, 152 and 152, respectively.

[figure not shown]
Study Population: Eligible patients will be 18 years or older and must have a positive test result for COVID-19 infection to and meet the inclusion criteria described in Section 4.1

Duration of Study: 24 months

Participant Duration: 30 days or in the case of hospitalization, upon discharge; whichever

is longer.

Schema: Convalescent Plasma Treatment for COVID-19 Infection

Definitions:

COVID-19 severity categories:

- Mild No pneumonia but with typical symptoms such as fever, dry cough, fatigue, nausea, emesis or diarrhea.
- Non-severe Radiographic changes compatible with viral PNA, but no signs of respiratory compromise or hypoxemia.
- •Severe Respiratory compromise with one of the following: Tachypnea with RR ≥30, O₂ Sat ≤93% at rest, PaO₂/FiO₂ index ≤ 300 mmHg
- Critical One of the following: requiring mechanical ventilation, requiring pressor support, multiorgan failure.

Patient Risk Category:

High risk:

- •Immunocompromised (e.g. neutropenia, h/o hematopoietic stem cell transplant (<3 months post-autologous transplant, <6 months post-allogeneic transplant), on systemic immunosuppression, h/o solid organ transplant, Cancer patient receiving active chemotherapy, insulin dependent diabetes mellitus, poorly controlled HIV, moderate or severe asthma history, serious heart condition, ESRD on hemodialysis, morbid obesity, moderately severe or greater COPD.
- •Age ≥ 65 years

Contents

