3.2 Number of Patients

The number of patients expected per each of the 2 groups:

Group 3: High Risk: n=159
Group 4: Health Care Providers: n=152

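### Group 3's maximum size is given as 219 in its own 6.1 paragraph but is 228 everywhere else, and its expected size is 152 in one place and 159 in four

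*Combined protocol and SAP*

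**What the plan says.** **Maximum size, Group 3.** The Group 3 paragraph of section 6.1 says "We will carry out 3-stage of enrollment and 76 patients are enrolled in each stage" and puts the interim analysis after outcomes on 76 patients. It then says "Our design leads to the maximum size of 219 patients after completing 3-stage of enrollment and the expected size is 159 patients". The table in 6.1 lists stages of 76, 76 and 76, a maximum of 228 and an expected enrolment of 159. The Overview of Study Design in the Protocol Summary lists the maxima as "Group 1: 81, Group 2: 423, Group 3: 228 and Group 4: 219".

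**Expected size, Group 3.** The same overview says "the expected numbers of enrollment for the four groups are 56, 296, 152 and 152, respectively", so Groups 3 and 4 share the value 152. The list at the front of the Protocol Summary has "Group 3: High risk patients n=159" and section 3.2 has "Group 3: High Risk: n=159". The 6.1 table and the Group 3 paragraph of 6.1 also give 159.

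**Where the maximum is used.** Section 6.3 says "The first interim analysis will be performed after enrolling and observing outcomes of one-third of maximum sample size", and section 6.1 has a similar sentence. Section 6.3 then applies a score confidence limit with critical value 2.289 to the cumulative data at each look, including the last.

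**The concern.** Three stages of 76 cannot make 219. The paragraph contradicts its own stage size as well as the table and the summary.

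The maximum is an operating number in this design. It decides when the third and last analysis is done and how many progressions still count as success. The trial is single-arm, with outcomes visible as they accrue. Two readings of the final sample size would leave room to choose between them once the event count is known.

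The first look is also defined as a third of the maximum. That is 76 for 228 and 73 for 219, and the paragraph itself says 76.

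The expected size triggers no decision. It is, however, the enrolment figure shown to readers at the front of the protocol, so it should agree across sections.

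**Working it through.** **Inputs.** From 6.1: 80% power, 5% overall type I error, three equally spaced looks, a large-sample Z test for one proportion; Group 3 null 25%, alternative 16.3%; Group 4 null 14.8%, alternative 7.5%. From 6.3: Pocock critical value 2.289.

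Two assumptions are mine. The error rate is taken as two-sided, because 2.289 is the two-sided 5% Pocock constant for three looks. The variance is taken under the null, because the documents give no variance formula.

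**1. Stage arithmetic.** 3 x 76 = 228. 3 x 73 = 219. The difference is 9 patients, and 9/228 = 3.9%.

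**2. Reproducing the 6.1 table.** The fixed-sample size is n = (1.960 + 0.842)² × p0(1 − p0) / (p0 − p1)². The three-look Pocock inflation factor at 80% power is 1.166, and the expected size under the alternative is 0.818 times the fixed size.

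| | Fixed n | × 1.166 | Per stage, rounded up | Maximum | Expected |
|---|---|---|---|---|---|
| Group 3 | 7.849 × 0.1875 / 0.087² = 194.4 | 226.7 | 76 | 228 | 159.1 |
| Group 4 | 7.849 × 0.1261 / 0.073² = 185.7 | 216.6 | 73 | 219 | 152.0 |

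All four table figures come back: 228 and 159 for Group 3, 219 and 152 for Group 4. At exactly 76 per stage, Group 3 has power 80.2% and expected size 159.7. With the unrounded alternative 0.65 × 25% = 16.25%, 76 per stage gives 80.7% and 159.0, although the formula alone would then ask for 75 per stage (225).

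**3. Power with 219, same method.** The final-look drift is √N × (0.25 − 0.163) / √0.1875. It is 3.034 at N = 228 and 2.973 at N = 219. Power is 80.2% at 228 and 78.6% at 219, whether 219 is reached as 76/76/67 (219 − 152 = 67) or as 3 x 73. At 3 x 73 the expected size is 155.6, which is neither 159 nor 152.

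**4. Success bounds under 6.3.** The upper score limit lies below 0.25 when (0.25 − x/n) / √(0.1875/n) exceeds 2.289.

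- N = 228: x = 42 gives 2.294 (success), x = 43 gives 2.141 (not).
- N = 219: x = 40 gives 2.302 (success), x = 41 gives 2.146 (not).
- First look, n = 76: x = 10 gives 2.384 (success), x = 11 gives 2.119 (not).
- First look, n = 73: x = 9 gives 2.500 (success), x = 10 gives 2.230 (not).

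**5. Exact binomial check of the 6.3 rule** (true rate 16.3% for power and expected size, 25% for type I error).

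| Stages | Bounds | Stop at first look | Power | Expected N | One-sided type I error |
|---|---|---|---|---|---|
| 76/76/76 | 10/76, 25/152, 42/228 | 28.7% | 84.8% | 160.5 | 2.2% |
| 76/76/67 | 10/76, 25/152, 40/219 | 28.7% | 83.1% | 156.9 | 2.1% |
| 73/73/73 | 9/73, 24/146, 40/219 | 22.8% | 83.0% | 159.2 | 2.0% |

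The exact expected size of 159.2 at 3 x 73 shows that 159 alone does not single out 228. The stage arithmetic does.

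**6. Expected size.** 152 appears once for Group 3 and 159 four times. The difference is 7 patients, and 7/159 = 4.4%.

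**The case against.** The strongest reply is that the documents nearly correct themselves. The table, the stage size and the summary all give 228, and anyone running the trial would work from the table. That makes the fix obvious, but it leaves a conflicting maximum in the paragraph that governs Group 3, and the documents state no order of precedence.

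The 73-patient first look is also an unlikely reading, since the Group 3 paragraph puts that look at 76 outright. This is fair. The more realistic alternative is 76/76/67, in which the first two looks are unchanged and only the final bound moves. Part of the gap between 28.7% and 22.8% comes from the discreteness of the binomial. The case rests on the final sample size.

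The practical effect is modest. At a true rate of 16.3% the third stage is reached about 40% of the time (exact), and type I error hardly moves. The overview sentence that gives 228 still lists Groups 1 and 2, which are no longer in the study, so it is weaker support than the table.

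Finally, a different variance choice (null at the boundary, alternative for power) needs only 213 to 216 patients in Group 3, close to 219. That does not rescue 219: the same choice gives 192 to 195 for Group 4, where the plan says 219, and 219 still cannot be three stages of 76.

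**Conclusion.** The concern holds. Group 3's maximum of 219 is wrong as written: it conflicts with the stage size in its own paragraph, with the 6.1 table and with the Protocol Summary. The expected size of 152 in the overview conflicts with 159 in four places. Both stray values equal Group 4's figures. A carry-over is the likely origin, but the documents do not say so.

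The final analysis is left ambiguous by 9 patients, with a success bound of 42/228 or 40/219. There is no type I error problem. Whether power stays above 80% with 219 depends on the method: yes by exact calculation of the 6.3 rule, no (about 78.6%) by the Z approximation that reproduces the plan's sizing. The Z figure rests on the null-variance assumption and on 16.3% as the alternative; the arithmetic contradiction rests on no assumption. The expected-size mismatch alone would be minor. The maximum should be corrected.

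**What to change.** - In the Group 3 paragraph of section 6.1, change the maximum from 219 to 228.
- In the Overview of Study Design in the Protocol Summary, change Group 3's expected enrolment from 152 to 159.
- State once, in 6.1, that Group 3's cumulative looks are at 76, 152 and 228 patients, and refer to that line wherever 6.1 and 6.3 time a look as a third of the maximum.

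The cost is two numbers and one line in an amendment. Both corrected figures already stand elsewhere in the documents, so planned enrolment does not increase and no analysis changes.

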In a larger report from Chinese Center for Disease Control and Prevention of 72,314 cases 14% presented with severe disease that was defined as dyspnea, respiratory frequency \geq 30, blood oxygen saturation \leq 93%, partial pressure of arterial oxygen to fraction of inspired oxygen ratio < 300, and/or lung infiltrates >50% within 24-48 hours.** Critical disease developed in 5% that resulted in respiratory failure, septic shock and/or multi-organ failure. In this report the case fatality rate (CFR) was 8.0% in patients age 70-79, 14.8% in patients over age 80, and 49% in critical cases. CFR was elevated among those with preexisting comorbid conditions: 10.5% for cardiovascular disease, 7.3% for diabetes, 6.3% for chronic respiratory disease, 6.0% for hypertension and 5.6% for cancer. A total of 1,716 infected were health care workers. Overall, 14.8% of health care workers developed severe or critical disease, and 5 deaths were observed.**

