3.1.2 Study Entry: Time from COVID-19 Infection Onset

3.1.2.1 High Risk group: Entry within 14 days of COVID-19 infection documentation.

Patients in the High-Risk group must present with either mild or non-severe disease for to be eligible for study entry; thereby, being identified early in the infection. These patients are to be entered and consented within 14 days of symptomatic COVID-19 infection documentation. Mild symptoms could include typical symptoms such as fever, dry cough, fatigue, nausea, emesis or diarrhea

3.1.2.2 Health Care Providers group: Healthcare worker must present with asymptomatic and with a positive NP swab; or mild or non-severe disease for to be eligible for study entry; thereby, being identified early in the infection. Asymptomatic patients must be enrolled within 14 days of the positive COVID-19 test. Mild or non-severe must be enrolled within 14 days of symptomatic infection documentation.

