4.1.2 Group 4: Health Care Providers with asymptomatic, mild or non-severe disease

- 1. Health care providers who as part of their activities from time to time are at risk to exposure to COVID-19 infection. This includes administrative staff and ancillary support staff associated with hospitals or ambulatory clinic facilities.
- 2. Asymptomatic is defined as having diagnosis of COVID-19 without symptoms or clinical findings.
- 3. Mild or non-severe disease: Refer above for definitions.
- 4. Informed consent signed within 14 days positive COVID-19 test.

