6.2 Secondary Endpoints

6.2.1

Secondary endpoints will be analyzed for potential efficacy and statistically compared to historical or matched controlled comparison population. For patients with severe disease, the expected rate of ICU admission is 19.%, with 38.7% requiring mechanical ventilation (14.5% invasive), 94.6% had radiographic abnormalities of the chest, 15.6% developing acute respiratory distress syndrome, and median hospital stay of 13 days. A total of 14% of patients with COVID-19 disease developed severe disease.

6.2.2

Impact of donor sera neutralizing antibody titer will be correlated to clinical outcome.

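### The Group 4 null of 14.8% is reported for infected health care workers overall and is not shown to be a progression risk among workers not yet severe; if some of those cases were already severe at a comparable time, the efficacy rule is tilted towards a claim

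*Combined protocol and SAP*

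**What the plan says.** Section 6.1 bases the Group 4 null on this sentence: "Among healthcare workers 14.8% of cases were classified as evolving to severe or critical per the Chinese epidemiological review". It postulates that plasma will "reduce the probability for progression from asymptomatic, mild or nonsevere disease to that of severe disease" by a factor of 0.5, to 7.5% or lower.

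The figure comes from section 1.2. "A total of 1,716 infected were health care workers", and the next sentence reads: "Overall, 14.8% of health care workers developed severe or critical disease, and 5 deaths were observed". No split by severity at diagnosis is given, and 1,716 appears to be the denominator only because the two sentences are adjacent.

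Group 4 admits only workers who are not yet severe. Section 3.1.2.2 says "Asymptomatic patients must be enrolled within 14 days of the positive COVID-19 test" and gives symptomatic workers 14 days from documentation of symptomatic infection. Section 4.1.2 asks for "Informed consent signed within 14 days positive COVID-19 test".

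There is no control arm. Section 6.3 concludes efficacy and ends enrolment in the group when the upper score limit (critical value 2.289) lies below the null, at 73, 146 or 219 patients. Section 8.7 lists interim efficacy as a ground for closing the study.

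**The concern.** The null and the trial population may have different denominators. A worker who was severe at diagnosis, or who became severe before the time at which a trial patient would be enrolled, could count in the 14.8% but could never enter Group 4. If there were such workers, the enrolled group would, all else equal, have an untreated progression risk below 14.8% even with inert plasma.

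The whole conclusion rests on this one number, because efficacy is declared by comparing a single-arm rate with it. A null that is too high raises the chance of a false claim, and part of that excess would fall at an interim look and stop enrolment. The later comparison with published historical experience in 6.3 has the same mismatch if it uses the same figure.

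**Working it through.** **Inputs.** From 6.1: null p0 = 0.148, target p1 = 0.075, three stages of 73, large-sample Z test, power 80%, overall type I error 5% (sidedness not stated). From 6.3: critical value 2.289 and the score-limit rule. The share s is not in the document and is an assumption throughout.

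**Step 1: the plan's own figure.** With the null variance, the standard deviation per patient is √(0.148 × 0.852) = 0.3551. The drift at look k is (0.148 − 0.075)√(73k)/0.3551, that is 1.76, 2.48 and 3.04. With 2.289 at each look this gives power 80.5%, and 73 is the smallest stage size that reaches 80%. The maximum of 219 is reproduced. Expected enrolment is 153.1 against 152 stated. The sample-size arithmetic is sound.

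**Step 2: the exact rule.** The upper score limit is below p0 when x < Np0 − 2.289√(Np0(1 − p0)).

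- N = 73: 10.80 − 6.94 = 3.86, so a claim at 3 events or fewer.
- N = 146: 21.61 − 9.82 = 11.79, so 11 or fewer.
- N = 219: 32.41 − 12.03 = 20.38, so 20 or fewer.

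An exact binomial recursion over the three looks gives a false-claim rate of 1.4% if 14.8% is the right null, and power of 86.4% at 7.5%.

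**Step 3: the untreated risk if s > 0.** Let s be the share of the 14.8% already severe by a comparable entry time. These workers leave both numerator and denominator, so

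untreated risk = 0.148(1 − s)/(1 − 0.148s).

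At s = 20% this is 0.1184/0.9704 = 12.2%.

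**Step 4: false efficacy with inert plasma, boundaries 3, 11 and 20 unchanged.**

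| Assumed s | Untreated risk | P(efficacy claim) | of which at an interim look |
|---|---|---|---|
| 0 | 14.8% | 1.4% | 0.8% |
| 5% | 14.2% | 2.5% | 1.4% |
| 10% | 13.5% | 4.3% | 2.2% |
| about 11.5% | 13.3% | 5.0% | 2.6% |
| 20% | 12.2% | 11.7% | 5.7% |
| 33% | 10.4% | 34% | 17% |
| 50% | 8.0% | 79% | 51% |

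The constant 2.289 is the two-sided 5% Pocock value, which leaves 2.5% in the efficacy direction. That level is reached at s of about 5%, and the stated 5% at about 11.5%.

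**Step 5: what an observed result would exclude.** The score upper limit at z = 2.289, and the s at which the untreated risk equals it:

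| Result | Upper limit | s |
|---|---|---|
| 3/73 | 13.2% | 12.7% |
| 11/146 | 14.1% | 5.2% |
| 20/219 | 14.6% | 1.6% |
| 16/219 (near the 7.5% target) | 12.4% | 18.5% |

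A claim right at the final boundary therefore tolerates very little mismatch, while a result near the design target tolerates a good deal more.

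**The case against.** The strongest reply is that s may be zero. Section 6.1 describes the cases as evolving to severe or critical, section 1.2 says the workers developed it, and the sources cited are not in view. Section 1.2 also varies its verbs: it writes "of 72,314 cases 14% presented with severe disease" for all cases but uses *developed* for critical disease and for health care workers. That is some evidence that presentation and later development are kept apart. Against it, section 6.2.1 states: "A total of 14% of patients with COVID-19 disease developed severe disease". If that is the same 14%, the two verbs are interchangeable, but 6.2.1 names no source, so this does not settle the matter either. What stands is that s = 0 is a permitted reading which the document does not establish.

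Second, the direction holds only with all else equal. Differences in age, comorbidity, care or the definition of severe between the source and the trial could add to the bias or offset it. This stands.

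Third, the plan already has partial safeguards. The Protocol Summary and item 1.1.2.1 under section 2.1 frame the objective against the reported case rate for Groups 3 and 4, which is close to a suitably modest claim. Section 6.3 also foresees reassessing progression rates on CDC updates. However, item 1.1.2.3 speaks of a lower risk of severe disease, and 6.3 still concludes efficacy of the treatment. The reassessment is tied to sample size and says nothing about the denominator, so an updated all-case rate would leave the same question open.

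Fourth, the score rule is conservative (1.4% under a correct null), so a small s does not breach the stated 5%. This stands and is built into the figures above.

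**Conclusion.** The concern holds as a conditional one. The document uses an overall rate as a risk conditional on not yet being severe, without showing that it is one. If s > 0 then, all else equal, the null is too high and the 6.3 rule favours an efficacy claim. Because that rule alone decides the conclusion and can stop enrolment, this is more than a missing detail, and it should be fixed before the first interim analysis.

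The size is unknown. A reader might infer that the 14.8% is known to contain workers severe at presentation, or that the real false-claim rate is 34% or 79%. The document supports neither. It gives no value of s, and those rates are assumed scenarios at s = 33% and 50%. Nor does it follow that the sample size was miscalculated: 219 reproduces from the plan's own inputs. Confidence is high that the denominator is unstated and that the mechanism works as described. The net direction depends on the two populations differing in nothing else that matters.

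**What to change.** Before the first interim analysis:

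1. State in 6.1 the denominator of the 14.8%, including whether workers already severe at diagnosis are counted.
2. Look for a rate among workers not severe over the trial's entry window of 0 to 14 days. There is no single entry day to match, and the document contains no such rate, so it may not be obtainable. Unless one is found and substituted, limit the Group 4 conclusion in 6.3 and item 1.1.2.3 to a progression rate below the reported all-case rate, in line with the reported-case-rate wording in the Protocol Summary and item 1.1.2.1. Align the efficacy-stop wording in 6.3 and 8.7.
3. Beside the planned score upper limit, report the lowest untreated rate that the result still excludes, and the false-efficacy rate over untreated rates from 14.8% down to about 8%.

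If the null is replaced, keep 219 and restate Group 4 power on one stated basis. On the exact basis the current design (14.8% to 7.5%) has 86.4%. If the halving is kept, power is 82% at a 13.3% null and 76% at 12.2%. If the 7.5% target is kept instead, it is 67% and 45%. These should not be set against the plan's 80%, which is a large-sample figure.

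The cost is wording, a literature or local-cohort search and a short sensitivity table. No patients are added. The downside is a weaker claim or a lower stated power.
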